Randomization, allocation, concealment, and blinding

Eligible participants will be randomized to 1 of the 3 intervention groups with an allocation of 1:1:1 through a permuted block randomization with a block size of 3 or 6 to prevent anticipation of assignment to the study condition. Concealment of allocation will be implemented. The project data analyst will use computer software (nQuery) to generate a randomization schedule, which will be kept in a sealed envelope. On the day of the assignment, a research assistant will assign qualified individuals to intervention groups. The allocation sequence assigns individuals in the order that they were scheduled for baseline assessment. Randomization will occur after informed consent is obtained and baseline assessments have been completed.

Project data analysts will be blinded to group allocation. All study assessors who collect study outcome measures will also be blinded to the main study design and group allocation. Blinding will be strictly maintained by emphasizing to assessors the importance of minimizing assessment bias and regular checking of the blinding status. Efforts will be also made to maintain separation between the study assessors and research assistants who deal with administrative activities and class safety monitoring, and between study assessors and class instructors who deliver the intervention classes. Because of the nature of the interventions, study participants and interventionists will not be masked to group allocation. Participants will be instructed not to reveal their group status to the assessment staff at any time during follow-up.

Intervention

The intervention for the trial consists of three exercise modalities: (a) cognitively enhanced tai ji quan, (b) standard tai ji quan, and (c) stretching exercise. Each is described below. The protocol, which is specified in detail via a teaching manual, requires that each intervention be implemented, by a qualified interventionist, twice weekly, for 60 minutes per session for a total of 24 weeks (6 months).

Cognitively enhanced tai ji quan

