Intervention classes will be closely monitored by research staff throughout the study period. Session-by-session attendance of the study participants will be recorded by research staff, regardless of participants' participation status, and this information on exercise adherence rate will be used as an indicator of intervention adherence across the three intervention groups. For each intervention group, there will be a total of 48 exercise classes to be completed over the 24-week intervention period. Accordingly, the average intervention adherence rate will be calculated as follows: number of intervention sessions attended during the 24 weeks divided by total number of sessions prescribed for the study, reported as a percentage.

Baseline measures

At baseline, demographic and other information about age, sex, ethnicity/race, income, education, living arrangements, medical conditions, health status, habitual physical activity, ³⁴ and residence location will be collected via a survey questionnaire. Body weight, assessed by a medical scale, and height, measured by with a ruler fixed on a wall, will also be ascertained. These data will be used to describe study population characteristics at baseline.

Statistical Analysis Plan (SAP)

Study aims

The study has the following primary and secondary aims.

Primary aim

To determine whether a cognitively enhanced tai ji quan intervention, in comparison to a standard tai ji quan intervention and an exercise stretching control, is more effective in improving global cognitive function and dual-task walking performance among community-dwelling older adults with MCI.

Primary hypothesis: We hypothesize that, at 6 months, cognitively enhanced tai ji quan training will result in greater gains in the primary outcomes of global cognition and dual-task gait performance than either standard tai ji quan or stretching control.

Secondary aim

To determine whether the effect resulting from the acute intervention phase can be sustained 24 weeks after training stopped.

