 - Participants' characteristics ascertained at baseline will be compared across intervention groups using independent samples or Wilcoxon rank sum tests, as appropriate, for continuous variables and a chi-square or Fisher's exact tests, as appropriate, for categorical variables. Although no significant differences are expected due to the randomized intervention assignment and the relatively large sample size, any variables found to be significantly different will be noted and accounted for, by controlling for them as covariates in supplements to the main analyses.
- *Time-specific and change scores*. Scores at each follow-up and change in mean scores from baseline at 24 weeks, by intervention group, for all outcome measures will be calculated and presented.
- *Intervention adherence, attrition, and retention*. Class attendance data will be calculated as the average number of scheduled intervention sessions (48 total) attended by participants across intervention groups. Study attrition and retention rates will also be calculated and reported, by intervention group, as the number of participants who completed the 24-week intervention and those who completed all scheduled study follow-up assessments.

Analysis populations

Efficacy analyses. The effect of intervention on the co-primary study outcomes will be evaluated using an intention-to-treat approach in which participants will be analyzed according to randomization assignment. A modified intention-to-treat analysis will be conducted that includes all participants who have undergone randomization and have completed all study follow-up assessments, regardless of their participation adherence status. Finally, a per-protocol analysis will include participants in the intention-to-treat population who have an overall class attendance rate of $\geq 75\%$ (out of the total planned 48 intervention class sessions) of their assigned exercise intervention.¹⁰

Co-primary endpoint analyses

To test the *Primary hypothesis*, we plan to use a generalized linear mixed model with random intercepts and fixed treatment effects for the primary outcomes. Specifically, we will determine the intervention effect through an analysis of a 3 (Group) by 3 (Time) mixed-effects model with repeated measures (follow-up time point) on the second factor (i.e., outcome measures assessed at baseline, 4 months [mid-point], and 6 months [intervention termination]).

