Interim analysis

We do not plan to perform any interim analyses for efficacy or futility. Instead, we will conduct interim monitoring performance with a focus on subject accrual, protocol adherence, intervention fidelity, data completeness and quality control, and intervention safety and analysis. Each is described below.

Subject accrual

We plan to conduct 10 staggered recruitment and enrollment waves, with approximately 35 participants planned at each wave, over 3.5 years of the 5-year project life. Each recruitment wave will be closely monitored at monthly staff meetings, with presentation of recruitment charts, to ensure we achieve our enrollment target. The accrual rate will be reviewed annually by research staff and will be reported to ORI IRB and the project Safety Officer appointed by NIA.

Protocol adherence

The overall intervention adherence (i.e., exercise class attendance) rate is defined as the sum of the total number of participants attending divided by the maximum number of 48 sessions planned, multiplied by 100, during the 6 months of active intervention. For the trial, the target adherence rate is \geq 75%. Class attendance across the three study conditions will be closely monitored on a weekly basis by research staff and reviewed on a monthly basis by key personnel of the project. Participants who miss two consecutive sessions will be contacted by phone to ascertain the reason(s) for their absences and to encourage them to return.

Intervention fidelity

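### The overall adherence formula has no participant count in its denominator, so its result is not a percentage and cannot be compared with the ≥75% target

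*Protocol*

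**What the plan says.** The same definition stands in three places: the Protocol under *Intervention adherence and attrition*, the SAP inside the Protocol under *Interim analysis*, item *Protocol adherence*, and the stand-alone SAP under the same item. Each defines the overall rate over the six-month intervention as "the sum of the total number of participants attending divided by the maximum number of 48 sessions planned, multiplied by 100", and each sets a goal of at least 75%.

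Other sections describe attendance differently:

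- Protocol, *Assessment of intervention adherence*: the average rate is "number of intervention sessions attended during the 24 weeks divided by total number of sessions prescribed for the study, reported as a percentage". This section also says that "there will be a total of 48 exercise classes to be completed over the 24-week intervention period" for each group, and that attendance is recorded whatever a participant's participation status.
- Protocol and SAP, *Descriptive analyses*: attendance is reported as the "average number of scheduled intervention sessions (48 total) attended by participants across intervention groups", which is a count and not a rate.
- Protocol and SAP, *Analysis populations*: the per-protocol set takes participants who attended at least 75% of the 48 planned sessions.

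The section on assessing adherence is not reproduced in the stand-alone SAP. There, the formula under *Protocol adherence* is the only one given for the overall percentage.

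**The concern.** The numerator is a count taken over many people, and the denominator is the number of sessions planned for one person. The ratio therefore grows with enrolment and has no upper limit of 100%, so setting it against 75% has no meaning. The documents also contain a second formula that gives a different answer for any group of more than one person, and nothing reconciles the two.

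Attendance is the main record of how much training each arm received, and readers need comparable rates by arm when they interpret differences between arms. Adherence is a named interim-monitoring item with a numerical target. Under *Statistical interim analyses and stopping guidance*, it is also among the grounds on which the Safety Officer judges whether data collection goes on. A figure with those uses needs one definition that can be computed.

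**Working it through.** The 75% is a target and not a derived result, so there is no stated figure to reproduce. The quantities around it do reproduce.

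**Inputs**

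- Sessions per participant: 2 per week × 24 weeks = 48, as stated.
- Sample size: 267 / (1 − 0.15) = 314.1, rounded up to 315, as stated under *Power estimation for primary outcomes*. With 1:1:1 allocation, 315 / 3 = 105 per arm.
- Recruitment wave: about 35 participants (*Subject accrual*).

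The wording of the numerator allows two readings. Let N be the number of participants and p the true share of sessions attended.

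**Reading A: attendances summed over sessions**

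Rate = (N × 48 × p) / 48 × 100 = 100 × N × p. This is the mean head-count per session, times 100.

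- Arm of 105 at p = 0.75: attendances = 105 × 36 = 3,780, and 3,780 / 48 × 100 = 7,875%.
- Wave of 35 at p = 0.75: attendances = 35 × 36 = 1,260, and 1,260 / 48 × 100 = 2,625%.
- Attendances needed to reach 75%: 0.75 × 48 = 36 in total. In an arm of 105 that is 36 / (105 × 48) = 36 / 5,040 = 0.7% true attendance.

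**Reading B: distinct people who attended**

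Rate = people attending / 48 × 100, and 75% again needs 36 people.

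- Arm of 105: 36 / 105 = 34% of the arm meets the target. The maximum is 105 / 48 × 100 = 219%.
- Wave of 35: the maximum is 35 / 48 × 100 = 73%, so the target cannot be reached even if everyone attends.

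**Comparison with the section on assessing adherence**

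Sessions attended over sessions prescribed, taken per participant and averaged, is bounded at 100%. An average of 36 of 48 sessions gives 75%. Reading A gives the same value only when N = 1.

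**With the participant count restored**

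Rate = total sessions attended / (48 × N) × 100. For an arm of 105 at p = 0.75, this is 3,780 / 5,040 × 100 = 75%. Because every participant is prescribed the same 48 sessions, it equals the mean of the individual rates.

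**The case against.** The best reply is that this is a drafting slip with an obvious intent. The section on assessing adherence, the descriptive analyses and the per-protocol rule all point to the mean share of 48 sessions attended. The formula for assessing adherence does not name a participant count either, so part of the conflict comes from reading one sentence literally and the other generously. This largely stands as to intent. It does not rescue the sentence itself, which is repeated three times, carries the target, and has no competing formula for the overall rate in the stand-alone SAP.

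A reader might infer three stronger things that the documents do not support.

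- **That the target is met at almost any attendance, so poor exposure would pass unseen.** The first part holds only on Reading A; on Reading B a wave could never meet the target. A result of 7,875% would be recognised at once as an error. The weekly attendance checks, the monthly review by key personnel and the telephone call after two consecutive missed sessions do not use the formula.
- **That people who stop attending are left out of the rate.** No section says so. The section on assessing adherence records attendance whatever the participation status and divides by prescribed sessions, which suggests that they are kept. An explicit statement would help, but its absence is only a missing detail.
- **That efficacy results are affected.** The per-protocol set has its own participant-level rule of at least 75% of 48 sessions, which is correctly scaled.

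**Conclusion.** The formula is wrong as written. On either reading it does not give a valid adherence percentage: an arm of 105 with 75% true attendance returns 7,875% when attendances are summed, and when people are counted the threshold is 36 individuals whatever the size of the group. It disagrees with the protocol's own alternative for any group larger than one.

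The consequence is limited to the adherence figure that is monitored and reported, including what reaches the Safety Officer. No efficacy analysis, significance level, sample size or per-protocol set depends on it. The figures assume equal arms of 105 and waves of 35, both taken from the plan. The correction should be made because it is nearly free and the target has no meaning without it.

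**What to change.** In all three places, replace the definition with: total sessions attended by all participants randomised to the arm, divided by (48 × the number randomised to that arm), times 100, reported by arm. Say in the same sentence that participants who stop attending stay in the denominator and that their missed sessions count as not attended. This agrees with the existing practice of recording attendance whatever the participation status. Align the protocol's section on assessing adherence with the same definition.

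The cost is one sentence in three places and an edit to a fourth. Session-by-session attendance is already recorded, so no new data collection is needed. Where an adherence figure has already been reported, state which definition produced it and recompute from the existing records if it differs.

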Statistical Plan

Last updated: September 12, 2024

Identifiers:NCT04070703

Unique Protocol ID: AG059546

Published in: [name], [name], [name], [name], [name]. Clinical effectiveness of cognitively enhanced tai ji quan training on global cognition and dual-task performance during walking in older adults with mild cognitive impairment or self-reported memory concerns: A randomized controlled trial. Ann Intern Med. 31 October 2023. [Epub ahead of print]. doi:10.7326/M23-1603

Supplement 1: Trial Protocol

Table of Contents

Statistical Analysis Plan	21-30
Data Management.....	31
Timing of Statistical Analysis	31

Statistical Analysis Plan (SAP)

Study aims

The study has the following primary and secondary aims.

Primary aim

To determine whether a cognitively enhanced tai ji quan intervention, in comparison to a standard tai ji quan intervention and an exercise stretching control, is more effective in improving global cognitive function and dual-task walking performance among community-dwelling older adults with MCI.

Primary hypothesis: We hypothesize that, at 6 months, cognitively enhanced tai ji quan training will result in greater gains in the primary outcomes of global cognition and dual-task gait performance than either standard tai ji quan or stretching control.

Secondary aim

To determine whether the effect resulting from the acute intervention phase can be sustained 24 weeks after training stopped.

Secondary hypothesis: We hypothesize that compared with standard tai ji quan or stretching control, participants in the cognitively enhanced tai ji quan training will retain their intervention gains in the primary outcomes of global cognition and dual-task gait performance at 12 months (post-intervention) follow-up. We also hypothesize that cognitively enhanced tai ji quan training will continue to be superior to either standard tai ji quan or stretching control, at 12-month follow-up, in terms of sustaining the training effect on slowing disease progression to dementia, as indexed by the continued improvement in the mean CDR-SB score from baseline.

Study design

This study is designed as a prospective, assessor-blinded, 3-arm parallel group, randomized clinical trial with a 1:1:1 allocation ratio. The primary co-outcome measures are global cognition function and dual-task walking costs. The target sample size is 315 participants, enrolled from local communities. The goal is to detect, with 80% power, 1.5 points in MoCA between the cognitively enhanced tai ji quan and the standard tai ji quan groups and 3 points between the cognitively enhanced tai ji quan and the stretching control groups at 24 weeks. The study will consist of a 6-month acute intervention phase (designed for addressing the primary aim) followed a 6-month maintenance phase (for addressing the secondary aim).

Outcomes

Table 1 below describes the study's primary, secondary, and tertiary outcomes, source of data, and follow-up schedule.

	Measure	Data source	Follow-up schedule
Primary outcome			
Global cognition	Montreal Cognitive Function measure (MoCA; score range: 0 to 30)	Assessment conducted by assessors	4 months, 6 months, and 12 months
Dual-task walking costs	Difference between single- and dual-task gait speed (expressed in percentage)	Assessment conducted by assessors	4 months, 6 months, and 12 months
Secondary outcome			

Cognition and function	Clinical Dementia Rating Sum of Boxes score (range: 0 to 18)	Interviews with participants and informants conducted by assessors	4 months, 6 months, and 12 months
Executive function	Trail Making Test (B) (measured in seconds)	Cognitive assessment conducted by assessors	4 months, 6 months, and 12 months
Attention and memory	Category Fluency (number of animal names recalled)	Cognitive assessment conducted by assessors	4 months, 6 months, and 12 months
Attention	Forward Digit Span (range: 1 to 16)	Cognitive assessment conducted by assessors	4 months, 6 months, and 12 months
Memory	Backward Digit Span (range: 1 to 16)	Cognitive assessment conducted by assessors	4 months, 6 months, and 12 months
Mobility	Timed Up&Go (measured in seconds)	Physical assessment conducted by assessors	4 months, 6 months, and 12 months
Lower-extremity strength	30-second chair stand test (number of times)	Physical assessment conducted by assessors	4 months, 6 months, and 12 months
Static balance	4-stage balance test (range: 0 to 4)	Physical assessment conducted by assessors	4 months, 6 months, and 12 months
Tertiary outcome			
Everyday cognitive function	Everyday Cognition Scale (range: 1 to 4)	Informant-rated questionnaire	4 months, 6 months, and 12 months
Depressive symptoms	Geriatric Depression Scale (range: 0 to 15)	Survey completed by participants	4 months, 6 months, and 12 months
Sleep quality	Pittsburgh Sleep Quality Index (range: 0 to 21)	Survey completed by participants	4 months, 6 months, and 12 months
Quality of life	EuroQol EQ-5D (range: -1 to 1)	Survey completed by participants	4 months, 6 months, and 12 months

Randomization

Method of randomization

Eligible participants will be randomized to one of the three intervention groups with an allocation of 1:1:1 through a permuted block randomization method with a block size of 3 or 6 to prevent anticipation of assignment to the study group. The project data analyst, who will not be involved in the recruitment of participants, will use computer software (nQuery, version 4.0, Statistical Solutions Ltd) to generate a randomization schedule, which will be kept in a sealed envelope. No one else on the project will be

involved in generating the randomization. The schedule will be released by the data team to a research assistant before each wave of recruitment is scheduled. On the day of the assignment, the research assistant will assign qualified individuals to the intervention groups. The allocation sequence assigns individuals in the order that they were scheduled for baseline assessment. Randomization will occur after informed consent is obtained and baseline assessments have been completed.

Allocation concealment

To control for selection bias, all study assessors who collect study outcome measures will be blinded to the main study design and group allocation. Blinding will be strictly maintained by emphasizing to assessors the importance of minimizing assessment bias and by random checking of the blinding status. Efforts will be also made to maintain separation between the study assessors and research assistants who deal with administrative activities and class safety monitoring, and between study assessors and class instructors who deliver the intervention classes. Because of the nature of the interventions, study participants and interventionists will not be masked to group allocation. Participants will be instructed not to reveal their group status to the assessment staff at any time during follow-up.

Statistical interim analyses and stopping guidance

None. However, annual data and safety information related to the project will be presented to the project Safety Officer appointed by the funding agency. The Safety Officer will determine whether any interim statistical analyses will be necessary and whether data collection continues on the basis of the project progression on subject recruitment, study assessment, or intervention adherence.

The following describes our pre-specified data analysis plan. Data will be coded to maintain group allocation blinding during analysis.

Descriptive analyses

- *Trial flow.* Information on the number of individuals screened, excluded, and qualified per the study eligibility criteria and assigned to the intervention, as well as the follow-up status, at each assessment time point will be presented in a figure in accordance with the CONSORT guidelines.
- *Comparability of intervention groups*
 - Baseline characteristics of the study population will be summarized by intervention group using summary statistics (e.g., mean, standard deviation, range, frequencies, or percentages) for continuous variables and frequency or percentages for categorical variables. Median IQRs will be calculated for variables that are not normally distributed.
 - Participants' characteristics ascertained at baseline will be compared across intervention groups using independent samples or Wilcoxon rank sum tests, as appropriate, for continuous variables and a chi-square or Fisher's exact tests, as appropriate, for categorical variables. Although no significant differences are expected due to the randomized intervention assignment and the relatively large sample size, any variables found to be significantly different will be noted and accounted for, by controlling for them as covariates in supplements to the main analyses.
- *Time-specific and change scores.* Scores at each follow-up and change in mean scores from baseline at 24 weeks, by intervention group, for all outcome measures will be calculated and presented.
- *Intervention adherence, attrition, and retention.* Class attendance data will be calculated as the average number of scheduled intervention sessions (48 total) attended by participants across intervention groups. Study attrition and retention rates will also be calculated and reported, by intervention group, as the number of participants who completed the 24-week intervention and those who completed all scheduled study follow-up assessments.

Analysis populations

Efficacy analyses. The effect of intervention on the co-primary study outcomes will be evaluated using an intention-to-treat approach in which participants will be analyzed according to randomization assignment. A modified intention-to-treat analysis will be conducted that includes all participants who have undergone randomization and have completed all study follow-up assessments, regardless of their participation adherence status. Finally, a per-protocol analysis will include participants in the intention-to-treat population who have an overall class attendance rate of $\geq 75\%$ (out of the total planned 48 intervention class sessions) of their assigned exercise intervention.¹⁰

Co-primary endpoint analyses

To test the *Primary hypothesis*, we plan to use a generalized linear mixed model with random intercepts and fixed treatment effects for the primary outcomes. Specifically, we will determine the intervention effect through an analysis of a 3 (Group) by 3 (Time) mixed-effects model with repeated measures (follow-up time point) on the second factor (i.e., outcome measures assessed at baseline, 4 months [mid-point], and 6 months [intervention termination]).

In the presence of a Group by Time interaction effect, follow-up pair-wise comparisons, using independent t tests, will be performed to identify a priori specified between-group differences. Specifically, we will determine the intervention effect of cognitively enhanced tai ji quan for change in MoCA and costs of dual task in gait performance from baseline to 24 weeks by making a comparison between cognitively enhanced tai ji quan and standard tai ji quan and between cognitively enhanced tai ji quan and stretching exercise.

Level of statistical significance and confidence intervals. Our primary outcome analyses will be 2-sided with an adjusted significance level of <0.0125 ($0.05 / 4$ comparisons) and a 98.75% confidence interval (CI). For each group, both estimated means and their corresponding standard error of estimates at each assessment point will be presented. In presenting between-group differences, mean differences with CIs will be presented. SPSS “MIXED” function will be used in analyzing our primary outcomes.

Secondary and tertiary outcome analyses

A similar analytic approach will also be applied to all secondary and tertiary (continuous) outcome variables described in Table 1. All study outcomes are expected to follow a normal distribution. In the case of deviation from normality, generalized estimating equations will be used to assess the effect of intervention over time. No Bonferroni correction will be made to account for multiple comparisons.

Level of statistical significance and confidence intervals. All tests and CIs will be 2-sided, and statistical significance will be defined as a P value of <0.05 . For each group, we will report both estimated means and their corresponding standard error of estimates at each assessment point. In presenting between-group differences at 24 weeks, estimated mean differences with CIs will be presented.

Analyses on examining intervention durability at 48-week follow-up

We will use the same analytic strategy outlined in our primary and secondary outcome analyses, with the exception of CDR-SB (described in detail below), to examine whether the intervention effects will persist 24 weeks after the end of the 24-week supervised interventions (*Secondary hypothesis*).

With the longitudinal data, we will test the hypothesis that the rate of improvement over time in the mean CDR-SB score, at 24-week post-intervention follow-up, will be greater in the cognitively enhanced tai ji quan group compared with the other two exercise groups. To test this hypothesis, we will use the latent growth curve modeling approach,³⁵ with maximum-likelihood estimation, analyzing the rate of change in the mean CDR-SB score defined by the four measurement time points: baseline, 16 weeks (mid intervention assessment), 24 weeks (end of intervention assessment), and 48 weeks (24 weeks post intervention follow-up).

[figure not shown]
Accordingly, we will operationalize our basic growth curve model with two latent growth factors: Intercept (defining the initial level of CDR-SB – baseline) and Slope (defining the rate of change over the course of the 48-week study period), with each factor being defined by the four time-specific CDR-SB

measures. A schematic representation of the planned latent growth model to be evaluated for each intervention group is shown in Figure 1. The factor loadings for the Intercept factor will be fixed with a constant value of 1 for all measurement points whereas the loadings for the Slope factor, defining the rate of change over time, will be fixed at 0 for CDR-SB at baseline, 1 for CDR-SB at 16 weeks, 2 for CDR-SB at 24 weeks, and * for CDR-SB at 48 weeks (where * indicating an undefined, free estimate at 48 weeks). All other model parameters to be estimated include latent Intercept mean and its variance, latent Slope mean and its variance, the correlation between Intercept and Slope (covariance), and error variance for each of the four time-specific measurements (shown as E's). The model estimation will include all available data derived from the trial, hence, an intent-to-treat approach.

The model estimation of change in CDR-SB will involve two steps. First, we will estimate an unconditional latent growth model (i.e., without the group predictor [e.g., cognitively enhanced tai ji quan group vs standard tai ji quan group]). This unconditional growth curve model allows us to examine the overall pattern of change in the CDR-SB score over time. Next, a group predictor (as a binary variable [1=cognitively enhanced tai ji quan group and 2=standard tai ji quan group]) is added to the model parameterization. By regressing the Slope factor on to the predictor of the group variable, this model will examine the pre-specified intervention effect of the cognitively enhanced tai ji quan training, compared with each of other two active groups, individually, on the rate of change in cognitive functioning trajectories. The schematic representation of this second latent growth model with the group, as a predictor, is shown Figure 2 (next page). For reporting purposes, we will present (a) latent slope mean for each group and (b) the regression coefficient relating group and the latent slope (with 95% CI). A negative slope mean for CDR-SB will indicate an improvement in cognitive functioning and, therefore, a lowering of the disease progression, whereas a positive mean slope will indicate deterioration in cognitive functioning.

A statistically significant regression coefficient indicates the difference in the rate of CDR-SB progression. All tests and CIs will be 2-sided, and statistical significance will be defined as a P value of <0.05 . The planned statistical analyses on change in CDR-SB will be performed in *Mplus* statistical software version 8.2 (Muthén & Muthén).

Figure 1. Latent growth curve model (intercept and slope) of change in CDR-SB over the 48-week study period

Note:

Intercept: defines the CDR-SB score at baseline

[figure not shown]
Slope: defines change or progression in the CDR-SB score from baseline to 48 weeks

*indicating an undefined, freely estimated loading at 48 weeks

Values in the squared box indicates observed value at each measurement time point

E1 through E4 represent measurement error at each measurement time point

Figure 2. Latent growth (intercept and slope) model for examining intervention effect on CDR-SB over the 48-week study period

Note: Group is a binary variable involving a comparison between cognitively enhanced tai ji quan and standard tai ji quan or cognitively enhanced tai ji quan and stretching exercise.

Post-hoc exploratory analyses

No pre-specified post-hoc exploratory analyses are planned.

Subgroup analyses

In light of the findings reported in prior studies,^{36,37} we also plan to conduct a series of subgroup analyses. Specifically, using a three-way interaction model that involves factors of Group, Time, and Subgroup, we will examine whether the expected between-group differences in the two primary outcomes are associated with pre-specified subgroups that include sex (1 = men, 2 = women), age (1 = 65-74, 2 = 75-84, 3 = 85+ years old), and level of education (1 = high school diploma or lower, 2 = college degree or higher). We are aware of the fact that these subgroup analyses are not powered statistically, and we will therefore interpret any statistically significant results with caution. All subgroup analyses are based on an alpha level of <0.05.

Power estimation for primary outcomes

This study is powered to detect a mean difference in change in the primary outcomes of MoCA and motor-cognitive dual-task gait performance between (a) the cognitively enhanced tai ji quan intervention and a standard tai ji quan intervention operationalized by TJQMBB,¹⁰ and (b) the cognitively enhanced tai ji quan intervention and a non-tai ji quan control condition – stretching – at 6 months, among older adults with MCI. We estimated the magnitude of the effect size (difference score divided by its pooled standard deviation) that is detectable with at least 80% power using a 2-sided 0.05-level test. We expect that participants in the cognitively enhanced tai ji quan intervention would experience a clinically meaningful improvement of at least 1 score unit in MoCA and a 10% reduction in dual-task costs on gait performance speed between the enhanced tai ji quan intervention and each of the two comparison arms. The following details the parameters used and results of our power analyses for each of the two primary outcomes.

MoCA. Assuming two (pre and post) repeated measurements and a between-level correlation of 0.7, the planned sample size of 267 participants would provide >80% power to detect a medium-size difference (Cohen d = 0.4) in mean MoCA change of 1.5 points (SD = 3.5) between the cognitively enhanced tai ji quan and the standard tai ji quan groups and a large-size difference (Cohen d = 0.8) of 3 points (SD = 3.5) between the cognitively enhanced tai ji quan and the stretching control groups at 6 months. No minimal clinically important difference (MCID) in MoCA has been established in the physical exercise literature, but our target estimate is close to that of 1.22 points established for the stroke patient population.³⁸

Dual-task gait performance. Using the same assumptions, at 6 months, we estimated a 10% reduction in dual-task walking costs between the cognitively enhanced tai ji quan and standard tai ji quan interventions and a 20% reduction between cognitively enhanced tai ji quan and stretching interventions. At the time of developing this research proposal, no MCID for reduction in costs in dual-task performance in gait is available. The target estimates calculated in this trial were inferred from our prior completed studies.^{10,12}

Taking into account a conservative 15% loss during the 6-month active intervention period, a total of 315 participants was planned for the study.

Treatment of noncompliance and missing data

All enrolled study participants will be followed until the trial period ends, whether or not the participant is still receiving or complying with the intervention. Primary endpoint analyses will be conducted according to the original randomization scheme in an intention-to-treat approach. We will use a multiple imputation data method for missing data. We plan to perform 10 sets of imputations. Variables without missing data to be used for prediction of imputed values on the study variables will include baseline measures of age, sex, level of education, MMSE, number of chronic conditions, and depression. The imputed data will be submitted to the same analytic model (i.e., linear mixed model) as the non-imputed observed data, and the results of each analytic model will be pooled across the 10 imputed data

sets. The secondary outcome analyses will also be conducted using the multiple imputation method described above. Tertiary outcome analysis will be conducted with observed data without imputation.

Interim analysis

We do not plan to perform any interim analyses for efficacy or futility. Instead, we will conduct interim monitoring performance with a focus on subject accrual, protocol adherence, intervention fidelity, data completeness and quality control, and intervention safety and analysis. Each is described below.

Subject accrual

We plan to conduct 10 staggered recruitment and enrollment waves, with approximately 35 participants planned at each wave, over 3.5 years of the 5-year project life. Each recruitment wave will be closely monitored at monthly staff meetings, with presentation of recruitment charts, to ensure we achieve our enrollment target. The accrual rate will be reviewed annually by research staff and will be reported to ORI IRB and the project Safety Officer appointed by NIA.

Protocol adherence

The overall intervention adherence (i.e., exercise class attendance) rate is defined as the sum of the total number of participants attending divided by the maximum number of 48 sessions planned, multiplied by 100, during the 6 months of active intervention. For the trial, the target adherence rate is $\geq 75\%$. Class attendance across the three study conditions will be closely monitored on a weekly basis by research staff and reviewed on a monthly basis by key personnel of the project. Participants who miss two consecutive sessions will be contacted by phone to ascertain the reason(s) for their absences and to encourage them to return.

